11.3 Adverse events associated with olaparib

11.3.1 Dose Modification and Toxicity Management for Olaparib

Any toxicity observed during the study could be managed by interruption of the dose of study treatment or dose reductions. Repeat dose interruptions are allowed as required, for a maximum of 4 weeks on each occasion. If the interruption is any longer, the study team must be informed. Study treatment can be dose reduced to 250 mg twice daily as a first step and to 200 mg twice daily as a second step. If the reduced dose of 200 mg twice daily is not tolerable, no further dose reduction is allowed, and study treatment should be discontinued. Once dose is reduced, escalation is not permitted.

Dose reductions and modification will be made as indicated in the following table. The descriptions and grading scale found in the revised NCI CTCAE version 5.0 will be utilized for dose delays and dose modifications. For guidance on dose reductions when concomitant strong or moderate CYP3A inhibitors cannot be avoided see Section 5.3 Concomitant Medications/Vaccinations.

Dose Modification Table

Dose Level	Olaparib Dose
0	300 mg BID
-1	250 mg BID
-2	200 mg BID
Further dose reduction	NA; Treatment discontinuation

Management of hematological toxicity

Management of anemia

Hemoglobin	Action to be taken
Hb < 10 but ≥ 8 g/dl (CTCAE Grade 2)	-Give appropriate supportive treatment and investigate causality. -Investigator judgement to continue olaparib with supportive treatment as clinically indicated (eg transfusion) or interrupt dose for a maximum of 4 weeks.
Hb < 8 g/dl (CTCAE Grade 3/4)	-Give appropriate supportive treatment (e.g. transfusion) and investigate causality. -Interrupt olaparib for a maximum of 4 weeks until improved to Hb ≥ 10 g/dl. -Upon recovery dose reduce to 250 mg twice daily as a first step and to 200 mg twice daily as a second step in the case of repeat Hb decrease.

Common treatable causes of anemia (e.g., iron, vitamin B12 or folate deficiencies and hypothyroidism) should be investigated and appropriately managed. In some cases, management of anemia may require blood transfusions. For cases where patients develop prolonged hematological toxicity (≥ 2 week interruption/delay in study treatment due to CTC grade 3 or worse anemia and/or development of blood transfusion dependence), refer to dedicated section “Management of prolonged hematological toxicities while on study treatment” for the management of these cases.

Management of neutropenia, leukopenia, and thrombocytopenia

Toxicity	Study treatment dose adjustment
CTCAE gr 1-2	Investigator judgement to continue treatment or if dose interruption, this should be for a maximum of 4 weeks; appropriate supportive treatment and causality investigation
CTCAE gr 3-4	Dose interruption until recovered to CTCAE gr 1 for a maximum of 4 weeks, and dose reduction to 250 mg twice daily as a first step and 200 mg twice daily as a second step

Adverse event of neutropenia and leukopenia should be managed as deemed appropriate by the investigator with close follow up and interruption of study drug if required.

Primary prophylaxis with Granulocyte colony-stimulating factor (G-CSF) is not recommended, however, if a patient develops febrile neutropenia, study treatment should be stopped and appropriate management including G-CSF should be given according to local hospital guidelines. Please note that G-CSF should not be used within at least 24 h (7 days for pegylated G-CSF) of the last dose of study treatment unless absolutely necessary.

Platelet transfusions, if indicated, should be done according to local hospital guidelines.

Study treatment can be interrupted for CTCAE grade 1/2 neutropenia or thrombocytopenia as per investigator’s judgement. In case of CTCAE grade 3/4 neutropenia, leukopenia or thrombocytopenia, study treatment should be interrupted for a maximum of 4 weeks. Study treatment can be restarted at the same dose if an adverse event of neutropenia, leukopenia or thrombocytopenia have been recovered up to CTCAE grade 1 or less. Any subsequent interruptions will require study treatment dose reductions to 250 mg twice daily as a first step and to 200 mg twice daily as a second step.

Management of prolonged hematological toxicities while on study treatment.

If a patient develops prolonged hematological toxicity such as:

- ≥ 2 week interruption/delay in study treatment due to CTC grade 3 or worse anemia and/or development of blood transfusion dependence
- ≥ 2 week interruption/delay in study treatment due to CTC grade 3 or worse neutropenia (ANC $< 1 \times 10^9/L$)

- ≥ 2 week interruption/delay in study treatment due to CTC grade 3 or worse thrombocytopenia (Platelets $< 50 \times 10^9/L$)

Weekly differential blood counts including reticulocytes and peripheral blood smear should be performed. If any blood parameters remain clinically abnormal after 4 weeks of dose interruption, the patient should be referred to hematologist for further investigations. Bone marrow analysis and/or blood cytogenetic analysis should be considered at this stage according to standard hematological practice.

Development of a confirmed myelodysplastic syndrome or other clonal blood disorder should be reported as an SAE and full reports must be provided by the investigator.

Management of non-hematological toxicity

Management of new or worsening pulmonary symptoms

If new or worsening pulmonary symptoms (e.g. dyspnea or cough) or radiological abnormalities occur in the absence of clear diagnosis, an interruption in study treatment dosing is recommended and a diagnostic workup should be performed to exclude pneumonitis. Initial workup should consider the inclusion of a clinical evaluation, high-resolution CT scan, ruling-out infection, pulse oximetry, and other appropriate laboratory workup. Pulmonary consultation is highly recommended. Guidelines for the management of patients with immune-related AEs including pneumonitis are provided above.

Following investigation, if no evidence of abnormality is observed on CT imaging and symptoms resolve, then study treatment can be restarted, if deemed appropriate by the investigator. If significant pulmonary abnormalities are identified, these need to be discussed with the Study Physician.

Management of nausea and vomiting

Events of nausea and vomiting are known to be associated with olaparib treatment. In study D0810C00019 nausea was reported in 71% of the olaparib treated patients and 36% in the placebo treated patients and vomiting was reported in 34% of the olaparib treated patients and 14% in the placebo treated patients. They are generally mild to moderate (CTCAE grade 1 or 2) severity, intermittent and manageable on continued treatment. The first onset generally occurs in the first month of treatment with the incidence of nausea and vomiting not showing an increase over the treatment cycles.

No routine prophylactic anti-emetic treatment is required at the start of study treatment, although it may be delivered. Patients should receive appropriate anti-emetic treatment at the first onset of nausea or vomiting and as required thereafter, in accordance with local treatment practice guidelines. As per international guidance on antiemetic use in cancer patients (ESMO, NCCN), generally a single agent antiemetic should be considered eg dopamine receptor antagonist, antihistamines, dexamethasone.

Renal Impairment

If subsequent to study entry and while still on study therapy, a patient's estimated CrCl falls below the threshold for study inclusion (≥ 51 ml/min), retesting should be performed promptly.

A dose reduction is recommended for patients who develop moderate renal impairment (calculated creatinine clearance by Cockcroft-Gault equation of between 31 and 50 ml/min) for any reason during the course of the study: the dose of olaparib should be reduced to 200mg BD.

Because the CrCl determination is only an estimate of renal function, in instances where the CrCl falls to between 31 and 50 mL/min, the investigator should use his or her discretion in determining whether a dose change or discontinuation of therapy is warranted.

Olaparib has not been studied in patients with severe renal impairment (creatinine clearance ≤ 30 ml/min) or end-stage renal disease; if patients develop severe impairment or end stage disease it is recommended that olaparib be discontinued.

Hepatic Impairment

If subsequent to study entry and while on study therapy, the patient develops hepatic impairment, the investigator should make every attempt to identify the underlying reason for the impairment.

Olaparib can be administered to patients with mild or moderate hepatic impairment (Child-Pugh Classification A or B) with no dose adjustment. Olaparib has not been studied in patients with severe hepatic impairment and is NOT recommended for use in these patients.

Management of toxicity due to either pembrolizumab or olaparib

Both olaparib and pembrolizumab treatment may be associated with the development of pneumonitis, hepatic impairment, and renal toxicity. For renal dysfunction and hepatic dysfunction follow the dose modification guidelines provided above for both olaparib and pembrolizumab.

Treatment with olaparib must be held for any grade of pneumonitis. Treatment with pembrolizumab must be held for pneumonitis \geq Grade 2 as outlined above. Hold treatment for new or worsening respiratory symptoms such as cough, dyspnea, fever, wheezing, or radiologic abnormalities; evaluate promptly. Discontinue treatment if pneumonitis is confirmed.

Interruptions for intercurrent non-toxicity related events

Study treatment dose interruption for conditions other than toxicity resolution should be kept as short as possible. If a patient cannot restart study treatment within 4 weeks

for resolution of intercurrent conditions not related to disease progression or toxicity, the case should be discussed with the Principal Investigator.

All dose reductions and interruptions (including any missed doses), and the reasons for the reductions/interruptions are to be recorded in the eCRF.

Study treatment should be stopped at least 3 days prior to planned surgery. After surgery study treatment can be restarted when the wound has healed. No stoppage of study treatment is required for any biopsy procedure.

Study treatment should be discontinued for a minimum of 3 days before a patient undergoes radiation treatment. Study treatment should be restarted within 4 weeks as long as any bone marrow toxicity has recovered.

MRI/MRI-guided biopsy

Patients will be counseled regarding the MRI biopsy, which is an FDA approved technique. Breast MRI biopsy is currently being offered to any patient that needs it at MSK both for high risk screening and in the context of a new diagnosis of breast cancer. The use of magnets to obtain chemical information has been studied previously with minimal side effects. As is the case for a standard MR exam, the presence of a pacemaker or aneurysm clips could pose a risk to the patient and patients with these contraindications will be excluded. A subject with sensitivity to noise or some neurological problems may have difficulty tolerating the MRI noise. Therefore it is recommended that patients talk to their referring physician regarding the noise of the MRI prior to taking part in the study. Some patients feel claustrophobic (afraid of enclosed spaces) in the MRI magnet.

Rare but Serious due to MRI:

Another possible hazard of the exam is localized heating of the body due to the radio waves used. If this were to happen, the patient would feel an intense heating or burning sensation. The patient will be asked to notify the MR technologist immediately. However, the MR scanner and the MR coil has been designed to prevent this from happening and there have been no reports of local heating in patients scanned to date. Because the MR instrument attracts iron, any iron-containing objects will accidentally fly into the magnet causing injury. Precautions have been made to prevent this from happening. The power absorbed in the tissue is limited by the manufacturer according to FDA guidelines. The manufacturer has made the necessary modifications to the imaging pulse sequences to stay within the FDA guidelines and, as at 1.5T, the 3.0T has a safety mechanism to prevent an imaging sequence from starting if power absorption limits are reached.

MRI Contrast injection/IV Needle Placement:

- Hematoma at the injection site
- Phlebitis;
- Bleeding;
- Infection;

- Bruising;
- Minor discomfort;
- Headache;
- Nausea;
- Vomiting;
- Hives;
- Temporary low blood pressure;
- Allergic-type reaction

Rare, but Serious due to MRI Contrast injection/IV Needle Placement:

Kidney impairment, details follow. Rare but severe adverse events occur in approximately 15/100,000 persons administered intravenous gadolinium. There is a risk of death in 1/100,000 persons. Precautions should be exercised for patients with severely impaired renal function or hemolytic anemia. The very unlikely possibility of a reaction, including anaphylactic-like or cardiovascular reactions, should be considered, especially for patients with a known sensitivity to gadolinium or history of asthma. Nephrogenic Systemic Fibrosis (NSF) or Nephrogenic Fibrosing Dermopathy (NFD), kidney disorders, may occur in patients with moderate to end-stage kidney disease (glomerular filtration rate $< 30 \text{ mL/min/1.73m}^2$) and in patients with renal dysfunction due to the hepatorenal syndrome or in the perioperative liver transplantation period after they have had an MRI scan with gadolinium-based MR contrast agents. NSF causes fibrosis of the skin and connective tissues throughout the body. Patients develop skin thickening that may prevent bending and extending joints, resulting in decreased mobility of joints. NSF usually starts in the lower extremities. Fibrosis can also develop in the diaphragm, muscles in the thigh and lower abdomen, and lung vessels.

Due to biopsy:

For the biopsy the patient will receive percutaneous epinephrine and lidocaine. Potential side effects include: pain, infection and local allergic reaction.

Anticipated adverse events are those that may be expected from tissue biopsy. This may include pain, bleeding, bruising, hematoma, infection or wound healing complications. In addition, if there is a complication from the biopsy (for example a hematoma), this could lead to the removal of a bigger piece of breast tissue at the time of surgery than would normally be done, which could impact the appearance of your breast after surgery.

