4.0 OVERVIEW OF STUDY DESIGN/INTERVENTION

4.1 Design

This trial is designed as a single-arm, open-label, non-randomized study with sample size calculated using the Simon two-stage minimax design. The primary endpoint is pathologically negative MRI-guided biopsy after neoadjuvant combination olaparib-pembrolizumab therapy at 12 weeks. Patients are eligible if they have newly diagnosed cT1c-3N0-3M0 invasive breast cancer, either triple negative according to ASCO/CAP guidelines or hormone receptor positive breast cancer with a germline mutation in BRCA1, BRCA2, PALB2, RAD51C, or RAD51D and have undergone a pre-neoadjuvant chemotherapy MRI.

At baseline, consented patients will undergo a research tumor biopsy and the index tumor volume will be quantified on the standard of care breast MRI. Patients will then receive olaparib and pembrolizumab for 6-12 weeks, followed by SOC chemotherapy +/- pembrolizumab and surgery. Depending on response to study therapy, the sequence of cytotoxic chemotherapy +/- pembrolizumab vs surgery will be determined by the primary clinical team. At the 6-week timepoint, all patients will undergo MRI for tumor assessment of interval response, which will be immediately followed by a concurrent MRI-guided biopsy. Similarly, at the 12-week timepoint, all patients who remain on olaparib/pembrolizumab for > 6 weeks will undergo another MRI for tumor assessment of interval response, which will be immediately followed by a concurrent MRI-guided biopsy.

At 6 weeks of treatment, the first study MRI will be performed, and treatment response will be assessed by comparing difference in tumor volume on this MRI to that measured on the pre-neoadjuvant chemotherapy MRI. Patients will be categorized as follows:

Group 1: Decrease in tumor volume

- 1a) Decrease in tumor volume of at least 50% ($\geq 50\%D$)
- 1b) Decrease in tumor volume of 0 to 50% ($< 50\%D$)

Group 2: Enlargement in tumor volume of 0 to 25% ($< 25\%E$)

Group 3: Enlargement in tumor volume of 25% or greater

All evaluable patients across the 4 categories will be included for the primary endpoint.

Patients who are responding (any decrease in tumor size, groups 1a and 1b above) will continue the study therapy for 6 additional weeks after the initial tumor

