h: Includes respiratory rate, pulse rate, systolic and diastolic blood pressure while the patient is in a seated position, and temperature. Record abnormalities observed at baseline. At subsequent visits, record new or worsened clinically significant abnormalities. For the first infusion, vital signs should be measured within 60 minutes prior to the infusion and, if clinically indicated, every 15 (+/- 5) minutes during and 30 (+/- 10) minutes after the infusion. For subsequent infusions, vital signs should be measured within 60 minutes prior to the infusion and, if clinically indicated or if symptoms occurred during the previous infusion, during and 30 (+/- 10) minutes after the infusion.

i: Includes evaluation of the head, eyes, ears, nose, throat, and the cardiovascular, dermatological, musculoskeletal, respiratory, gastrointestinal, and neurological systems. Record abnormalities observed at baseline. At subsequent visits, record new or worsened clinically significant abnormalities. At subsequent visits perform a limited, symptom-directed examination at specified timepoints and as clinically indicated at other timepoints. Record new or worsened clinically significant abnormalities.

j: See Appendix A.

k: ECG recordings will be obtained during screening and as clinically indicated. Patients should be resting in a supine position for at least 10 minutes prior to ECG recording.

l: Cardiac monitoring (ECHO or MUGA scan) will be performed on all patients enrolled in the study at baseline. ECHO is the preferred method. The same method used for a given patient a screening should be used throughout the study if clinically indicated.

m: Hematology includes WBC count, RBC count, hemoglobin, hematocrit, platelet count, and differential count (neutrophils, eosinophils, basophils, monocytes, lymphocytes, other cells). Chemistry panel (serum or plasma) includes sodium, potassium, chloride, bicarbonate or total CO₂, glucose, BUN or urea, creatinine, total protein, albumin, calcium, total bilirubin, alkaline phosphatase, ALT, AST. Magnesium and phosphorus should be included at screening and as clinically indicated during study treatment. Screening laboratory test results must be obtained within 14 days prior to initiation of study treatment. CBC/CMP will also be taken at week 3 during Cycle 1.

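### Section 11.3.1 gives two olaparib restart doses after a first grade 3-4 neutropenia, leukopenia or thrombocytopenia and, as a lesser point, cites a creatinine-clearance entry limit that Section 6.1 does not contain

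*Combined protocol and SAP*

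**What the plan says.** **Cytopenias, Section 11.3.1.** The grade 3-4 row of the table for neutropenia, leukopenia and thrombocytopenia calls for interruption until grade 1 "for a maximum of 4 weeks, and dose reduction to 250 mg twice daily as a first step", with 200 mg twice daily as the second step. It makes no exception for a first event.

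The text below the table covers the same three toxicities at the same grades. It sets the same 4-week limit on the hold, then says "Study treatment can be restarted at the same dose if an adverse event of neutropenia, leukopenia or thrombocytopenia have been recovered" to grade 1 or less. It adds: "Any subsequent interruptions will require study treatment dose reductions to 250 mg twice daily as a first step".

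Three other statements in Section 11.3.1 bear on this:
- "Adverse event of neutropenia and leukopenia should be managed as deemed appropriate by the investigator". This names no grade or dose and leaves out thrombocytopenia.
- For hemoglobin below 8 g/dl: "Upon recovery dose reduce to 250 mg twice daily as a first step", with 200 mg twice daily for a repeat fall.
- "Once dose is reduced, escalation is not permitted".

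**Renal function.** The renal paragraph of Section 11.3.1 describes a clearance of at least 51 mL/min as the inclusion threshold. It recommends 200 mg twice daily at 31-50 mL/min, subject to investigator discretion, and stopping olaparib at 30 mL/min or below. Section 6.1 instead admits creatinine up to 1.5 times the upper limit of normal or, if creatinine is higher, a clearance of at least 30 mL/min.

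**The concern.** A restart dose after a severe cytopenia is a safety instruction and should have one answer. Here, two investigators who each follow a line of the same section can restart the same patient at different doses. Because a toxicity reduction cannot be reversed, the choice lasts for the rest of a short course: "Patients will then receive olaparib and pembrolizumab for 6-12 weeks".

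Safety and tolerability is a secondary objective (Section 2.0), and Section 11.3.1 requires every reduction to be recorded. The count of reductions would then partly reflect which line was followed rather than how well the drug was tolerated.

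The renal mismatch is of the same kind but smaller: a management rule refers back to an entry limit that was never set.

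**Working it through.** The plan states no figure on this point to reproduce, so the check is a comparison of texts plus dose arithmetic.

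**1. The two cytopenia rules side by side (Section 11.3.1, grade 3-4)**

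| | Table row | Text below the table |
|---|---|---|
| Hold | Until grade 1, at most 4 weeks | At most 4 weeks |
| Restart after first recovered event | 250 mg twice daily | Same dose allowed (300 mg twice daily if not yet reduced) |
| Recurrence | Reduction | Reduction required |

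They agree on the hold, its limit and reduction on recurrence. They differ on the dose after the first recovered event.

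**2. Daily dose**
- Text: 2 x 300 = 600 mg/day (the starting dose in Section 5.2).
- Table: 2 x 250 = 500 mg/day.
- Difference: (600 - 500) / 600 = 16.7%.

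**3. Cumulative dose, as an illustration only**

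Assume that the event is found at a scheduled count and that missed doses are not made up. The scheduled on-treatment counts are at week 3 ("CBC/CMP will also be taken at week 3 during Cycle 1") and at the start of cycle 2, week 6.

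Difference = 100 mg/day x 7 x (course weeks - onset week - hold weeks).

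Planned totals: 84 days x 600 mg = 50.4 g for 12 weeks; 42 days x 600 mg = 25.2 g for 6 weeks.

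| Course | Onset | Hold | Days | Difference | Share of planned total |
|---|---|---|---|---|---|
| 12 weeks | Week 3 | 1 week | 56 | 5.6 g | 11.1% |
| 12 weeks | Week 3 | 3 weeks | 42 | 4.2 g | 8.3% |
| 12 weeks | Week 6 | 1 week | 35 | 3.5 g | 6.9% |
| 12 weeks | Week 6 | 3 weeks | 21 | 2.1 g | 4.2% |
| 6 weeks | Week 3 | 1 week | 14 | 1.4 g | 5.6% |
| 6 weeks | Week 3 | 3 weeks | 0 | 0 g | 0% |

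A 1-week hold needs an unscheduled count to show recovery. On scheduled counts alone, a week-3 event is next checked at week 6, which is the 3-week row. Section 11.3.1 allows holds of up to 4 weeks, but Section 12.0 says that a delay beyond 3 weeks may lead to discontinuation. There would then be no restart dose to compare, so longer holds are not shown.

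**4. How many patients**

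Section 15.0 lists low neutrophils and leukopenia in a band of more than 10 and up to 65 per 100 people, and low platelets in a band of 1 to 10 per 100. Each band is shared with other side effects, and no grade is given. Neither yields a grade 3-4 rate.

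**5. Renal limits**
- Section 6.1 with creatinine at or below 1.5 x ULN: no clearance floor.
- Section 6.1 with higher creatinine: floor of 30 mL/min.
- Section 11.3.1: cited entry threshold of 51 mL/min, a gap of 51 - 30 = 21 mL/min.
- A patient with raised creatinine and a clearance of exactly 30 mL/min meets Section 6.1, yet falls in the band where Section 11.3.1 recommends stopping olaparib.

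**The case against.** **The text only permits a same-dose restart.** This is true, and it stands: an investigator who follows the table breaches neither rule. A reader might infer that the two rules cannot both be satisfied, and that is not so. But a restart at 300 mg twice daily is allowed by the text and departs from the table.

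**Section 11.3.1 says that modifications follow the table.** That opening sentence introduces the dose-level ladder (300, 250, 200 mg). The ladder lists levels and does not say when to step down after a cytopenia. It suggests that tables are meant to be operative but does not settle the matter.

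**The steps in the cytopenia row may refer to later events.** The row is less explicit than the anemia rule, which ties reduction to recovery and the second step to a repeat fall. Still, it joins the hold and the reduction without any condition, and the natural reading is reduction at the first event. Which direction to harmonize remains partly a clinical choice.

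**Investigator discretion covers it.** That sentence adds a third reading and omits thrombocytopenia.

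**The renal point is mostly a labeling error.** Much of this stands. The retest trigger carries its own number and works at 51 mL/min whatever Section 6.1 says. The MRI contraindications appendix bars renal impairment, known or suspected, and leaves GFR requirements to local practice. Exclusion 19 lets the investigator exclude for a laboratory abnormality. A reader might infer that patients at 31-50 mL/min would routinely enter at full dose; the documents do not support that. These screens narrow the gap, but none gives a number.

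**Conclusion.** The main point holds. After a first grade 3-4 neutropenia, leukopenia or thrombocytopenia that recovers, Section 11.3.1 gives 500 mg/day by the table and permits 600 mg/day by the text in a patient not yet reduced. The table dose is 16.7% lower, with no re-escalation after the reduction. That figure needs no assumption; the cumulative figures rest on the assumed onset and hold times.

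Two stronger readings are not supported:
- **A count of affected patients.** Applying the Section 15.0 bands to 23 patients would not give one, because they are shared, ungraded bands and low platelets sit in a lower one.
- **Damage to the primary analysis.** Olaparib dose enters neither the definition of the primary endpoint nor the two-stage calculation in Section 14.0. Exact binomial sums for that design give a type I error of 0.046, power of 0.802 and an early-stopping probability of 0.605 under the null, in line with the stated 0.05, 0.80 and 0.60.

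The renal mismatch is real but minor. The cited 51 mL/min threshold is absent from Section 6.1, and a clearance of exactly 30 mL/min is both admissible at entry and a recommended stopping level. Both points concern conduct and patient safety and are worth correcting at the next amendment.

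**What to change.** **Cytopenias.** Delete the same-dose restart sentence and reword the one after it to match the table: 250 mg twice daily after the first grade 3-4 event, then 200 mg twice daily, as the anemia rule already does. State that the investigator-discretion sentence does not override the table at grade 3-4. The cost is amendment wording and a lower dose for some patients after a first event.

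**Renal function.** State a creatinine clearance of at least 51 mL/min in Section 6.1. This agrees with the renal paragraph of Section 11.3.1 and with the MRI appendix. It tightens eligibility slightly in a trial that expects 1-2 patients per month (Section 14.0). Admitting patients at 31-50 mL/min on a reduced starting dose is not a good alternative, because it would conflict with the appendix's bar on renal impairment.

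Neither change affects the sample size, visit schedule or analysis.
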